Appendix A: Scorecard

SUMMER SCORECARD

June-August 6

For each activity you complete:

1. Write the date.
2. Have your parent or guardian initial the box or get a Fit Kids stamp at the front desk when you check in at the Aquaplex, Cabin Fever, Flagstaff Athletic Club (FAC) or Jay Lively Activity Center.

Each activity is worth three points. Earn bonus points for completing more activities!

- **Complete 12 for 40 points (four bonus pts.)**
- **Complete 18 for 60 points (six bonus pts.)**
- **Complete all 24 for 80 points (eight bonus pts.)**

Activities must be completed by Sunday, Aug. 6. Turn in your Scorecard to Fit Kids staff during the month of August to receive your points.

Fit Kids Summer Series Bowling
	
Fit Kids Summer Series Running Club
	
Swim and play at FAC
	
Hike Fat Man's Loop 3 bonus points for a picture along the trail!
	BONUS

Family swim at FAC East 2 bonus points for a family picture!
	
Hike one of the Campbell Mesa Trails
	
Ride your bike for 60 minutes
	
Play a sport for 60 minutes If you're on a team, practice or games count!
	

Ice skating at Jay Lively
	
Your choice 60 minutes of activity
	
CrossFit Kids workout
	
Explore the lava tubes 3 bonus points for a picture in the cave!
	

Walk the big loop at Buffalo Park 2 bonus points for a picture with the buffalo!
	
Go to: NEW ROOTS FLAGSTAFF, AZ Summer Series Class
	
Flagstaff Community Market Local flavor at root level!
	
Family swim at FAC East
	

Play a sport for 60 minutes If you're on a team, practice or games count!
	
Hike Sedona's Red Rocks 3 bonus points for a picture along the trail!
	
Swim and play at Flagstaff Aquaplex
	
5K Walk/Run 2 bonus points for participating in the Machine Solutions Run for Kids on Aug. 5. Fit Kids get free entry!
	

CABIN Fever Laster tag, climbing and inflatables
	
Hike Mt. Humphreys 10 bonus points for a picture at the summit!
	
Your choice 60 minutes of activity
	
Round of Disc Golf

COVER PAGE

Study Title: Addressing Health Disparities in Childhood Obesity, One Summer at a Time

Clinical Trials Registration Number: NCT03595332

Date of document: July 14, 2022

Statistical Analysis Plan

The proposed statistical analyses for the current study includes a nested regression model utilizing Generalized Estimating Equations with an exchangeable working correlation matrix to account for the nested data structure of children within schools and families. For all variables, 95% Confidence intervals will be reported (for b in models with a linear response variable and Odds Ratios for models with an ordinal logistic response variable) and a significance level of $p=0.05$ will be used to test hypotheses.

For the primary analysis, we propose to test the difference in Body Mass Index (BMI) Percentile-scores for age and sex based on Centers for Disease Control and Prevention (CDC) criteria from Baseline to 10-weeks using GEE models with a linear response variable. We will test whether the difference is significantly different from zero, adjusting for age (included as a covariate) and sex and ethnicity (included as factors). We will also test whether the immediate intervention group was significantly different from the delayed intervention group by including a variable denoting immediate vs delayed group membership. We will test the null hypothesis that participants in the intervention did not significantly change their BMI Percentile-score.

For the second primary analysis, we will test whether the BMI Percentile from baseline to 10-weeks was significantly different from zero among the highest-risk children, defined as those participants with a baseline BMI Percentile score equal to or greater than the 85th percentile as considered by the Centers for Disease Control and Prevention. GEE models will be used restricting the sample to children with overweight at baseline.

For the first secondary analysis, we propose to test the difference in Body Mass Index Percentile-score from Baseline to 1-year follow-up using GEE models with a linear response variable. We will test whether the difference is significantly different from zero, adjusting for age (included as a covariate) and sex and ethnicity (included as factors). We will test the null hypothesis that participants in the intervention did not significantly change their BMI Percentile-score.

For the additional secondary analyses, we propose to test the difference in average self-efficacy score (1-5) from Baseline to 10-week follow-up using GEE models with an ordinal logistic response variable. We will test whether the difference is significantly different from zero, adjusting for age (included as a covariate) and sex and ethnicity (included as factors). We will test the null hypothesis that participants in the intervention did not significantly change their average self-efficacy score.

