Sample Size calculations: The estimated sample size needed to have sufficient power to detect a moderate effect size (using a Cohen's d of 0.3 as the reference) is 240 children, or 120 per arm. Based on our preliminary data, for each academic year, the average BMI change ranges from 0.35 to 0.55 units, with a standard deviation that varies across ethnic groups and years from 0.80

to 1.00. An example of an effect between two groups or time points that would match a Cohen's d of 0.3 would be one group in which the children on average increases their BMI by 0.5 units, and another group where participants increase their BMI by 0.2 units (0.3 unit difference), with standard deviations of 1.0. These effects (BMI difference of 0.3kgm^2) are just above the mean weighted effect size reported in the most comprehensive and recent meta-analysis on childhood obesity studies of 0.30kg/m^2 .^{9,10} With a two-tailed test and alpha level of 0.05, a sample size of 80 children per arm (a retention rate of 67%) would result in an associated statistical power $\geq 80\%$ to detect intervention effects between arms from one time point to the next. With very similar parameters and sample sizes, prior research has indicated that based on simulation studies,¹⁷ these parameters demonstrated excellent power ($\geq 80\%$) in detecting these size differences.

Institutional Review Board:

All protocol activities were approved by the Institutional Review Board of Northern Arizona University (protocol #1193689) and the Flagstaff Unified School District. Parental consent forms and children assent were attained for each participant.

References:

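### The SAP's exchangeable GEE names no child level and no response form; if both readings are stacked, the planned one-third loss can widen and bias the estimated BMI change

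*SAP*

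**What the plan says.** The opening paragraph of the SAP sets one structure for all models: GEE "with an exchangeable working correlation matrix to account for the nested data structure of children within schools and families". The levels named are school and family. Repeated readings on a child are not mentioned, and the cluster unit, the type of standard error and the handling of children without a second reading are not stated.

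Every analysis nevertheless concerns two readings on the same child:

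- The first primary analysis is to "test the difference in Body Mass Index (BMI) Percentile-scores for age and sex" "from Baseline to 10-weeks using GEE models with a linear response variable". The test is worded "We will test whether the difference is significantly different from zero, adjusting for age (included as a covariate"), and the arms are compared "by including a variable denoting immediate vs delayed group membership".
- The second primary analysis repeats this in children at or above the 85th percentile at baseline.
- The first secondary analysis runs "from Baseline to 1-year follow-up using GEE models with a linear response variable".
- The additional secondary analysis tests "the difference in average self-efficacy score (1-5) from Baseline to 10-week follow-up using GEE models with an ordinal logistic response variable", and the opening paragraph promises odds ratios for ordinal models.

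The Protocol, under Sample Size calculations, enrols 120 per arm and bases its power on "a sample size of 80 children per arm (a retention rate of 67" per cent).

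**The concern.** The SAP can be read in two ways. In one, each child contributes a single change score, and school and family are the complete nesting. In the other, both readings enter as responses and the change is a time coefficient. The second reading is realistic. A 1-5 score modelled ordinally and reported as an odds ratio most naturally has both readings in the response, because a change score does not lie on a 1-5 scale. For BMI, a covariate-adjusted test of zero change also fits a time coefficient; with a change score the test would be on an intercept that refers to age 0 unless age is centred, and the SAP does not mention centring.

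Under the second reading, a single exchangeable correlation must serve both a child's own two readings (highly correlated for BMI percentile) and readings on siblings or schoolmates (weakly correlated). The fitted value is a compromise, too low for the within-child pair. With complete pairs the point estimate is unaffected. With a third of the second readings missing, the model does not use each leaver's baseline properly. The estimated change loses precision, and it shifts if leavers differ from stayers in level. If heavier children leave, the artefact is a fall in percentile, which would look like benefit.

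**Working it through.** **Inputs from the documents.** 240 children, 4 schools, 80 of 120 per arm retained. The retention figure reproduces: 80/120 = 66.7%, so f = 1/3 are lost and 160 of 240 have both readings. The power attached to that figure is a separate matter and is not used here.

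**Assumed inputs (not in the documents).** Percentile SD 28; within-child correlation r = 0.95 (range 0.90 to 0.97); sibling correlation about 0.30 to 0.33; school ICC 0.02 to 0.03 (also 0.10); 33% to 40% of children in two-child families (also none). True change is 0 throughout.

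**Precision, loss unrelated to weight.** With school clusters the fitted correlation is near zero, so the estimate is close to the stayers' follow-up mean minus everyone's baseline mean:

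- Stacked, school clusters: SE = 28 × √(1/160 + 1/240 − 2 × 0.95/240) = 28 × √0.0025 = 1.40.
- One change score per child: SE = 28 × √(2 × 0.05/160) = 28 × √0.000625 = 0.70.
- Ratio 1.40/0.70 = 2.0, so (0.70/1.40)² = 25% of the information is kept.

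For any r the squared ratio is (5 − 4r)/(6(1 − r)), which gives SE ratios of 2.5 at r = 0.97, 2.0 at 0.95, 1.5 at 0.90 and 1.0 at 0.50. The loss of precision therefore belongs to highly correlated outcomes.

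Simulated SE of the change with random one-third loss, in three runs with slightly different assumptions:

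| Run | School | Family | Child | Change score |
|---|---|---|---|---|
| 1 | 1.33 | 0.88 | 0.65 | 0.65 |
| 2 | 1.39 | 0.96 | 0.70 | 0.71 |
| 3 | 1.2 | 0.9 | 0.7 | – |

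Against the child level the ratios are 2.0, 2.0 and 1.7 for school, and 1.35, 1.37 and 1.3 for family. With no loss, all four estimates in run 2 had SE 0.58.

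**Bias, loss related to baseline.** Let g be the baseline excess of leavers over stayers and a the fitted working correlation. Stayers' baseline mean lies f·g below everyone's, and their follow-up mean lies r·f·g below. The model gives back a·f·g, so the bias is about −f·g·(r − a).

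- School, a = 0.025, g = 0.48 × 28 = 13.44: −(13.44/3) × (0.95 − 0.025) = −4.48 × 0.925 = −4.1. Simulated: −4.17.
- Family, a about 0.66: −4.48 × 0.29 = −1.3. Simulated: −1.65. The formula is rougher here because it ignores the sibling terms.
- Child, a about 0.95: about 0. Simulated: −0.09.
- One change score, stayers only: +f·g·(1 − r) = 4.48 × 0.05 = +0.22. Simulated: +0.18.

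At gaps of 0.25 and 0.84 SD the simulated shifts were −2.2 and −7.3 (school), and −1.0 and −3.0 (family). At g = 0.48 SD the family-cluster test rejected the true null 45% of the time, against 6% at child level and 6.5% with change scores. School rejection rates are left out because they also carry the defect of a sandwich over four clusters.

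**Sensitivity.** With r from 0.90 to 0.97, or school ICC 0.10, the shift at a gap near 0.47 SD stayed between −3.75 and −4.2 (school) and between −1.4 and −1.65 (family). With no siblings the family cluster is the child cluster and its bias is 0.01, but the school cluster still gives −4.04. With 10% and 20% loss the shifts were −1.5 and −2.6 (school), and −0.6 and −1.0 (family).

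**The case against.** The strongest reply is that for BMI the SAP means one change score per child. The nesting phrase has children as its lowest unit, which is complete for one record each. The arm comparison adds a group variable with no time or group-by-time term; that tests a difference in change only if the response is a change, whereas with stacked readings it would test level. The Protocol's sample size is also expressed in BMI change. This is a fair reading and removes the problem entirely. It is not stated, though, and an analyst could follow the SAP as written and stack the readings.

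Second, the best textual evidence for stacking concerns self-efficacy, while every figure above is for BMI percentile in a linear model. No ordinal model was run. If a short survey scale has a within-child correlation near 0.5 (an assumption), the formula shows no loss of precision, and a linear simulation gave a bias of −0.05 SD with family clusters against −0.04 with child clusters. This objection stands: the sizes must not be carried over to self-efficacy.

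Third, nothing in the documents says that leavers are heavier, or that children with only a baseline reading enter the model; 67% retention is a planning allowance. Nor is the share of siblings given. These points also stand, and they make the bias conditional.

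A reader might infer that the primary BMI result is bound to be biased in the programme's favour. The documents do not support that: it requires stacked readings, baseline-only children in the model, and loss related to baseline level, none of which they settle.

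**Conclusion.** The point holds in conditional form. The SAP leaves out the child level and does not state the response. If both readings are stacked under one school- or family-level exchangeable correlation, the within-child correlation is understated, and the planned one-third loss makes the time effect partly a comparison of different children. For BMI percentile, at SD 28 and r = 0.95, the standard error is about 2 times (school) or 1.3 to 1.4 times (family) that at child level. If leavers start 0.48 SD heavier, a true zero change appears as about −4 points (school) or −1.7 (family).

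The mechanism is firm; the sizes are illustrative. They shrink as the within-child correlation falls and, for family clusters, as the sibling share falls. A reader might apply them to the second primary analysis, but baseline values there span at most 100 − 85 = 15 points, so the baseline SD cannot exceed 7.5 and figures computed at SD 28 do not apply. With one change score per child the problem is absent; what remains is a small regression-to-the-mean term, about +0.2 points in the example. The clarification is worth making because it is cheap and touches the primary analysis.

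**What to change.** - **BMI analyses (10 weeks, the subgroup, 1 year).** State that the response is one record per child, the change from baseline. Centre the covariates so that the intercept is the mean change. Use the GEE exchangeable correlation only between children of one family.
- **Self-efficacy.** If both readings are stacked in the ordinal model, make the child the working-correlation unit and use robust standard errors clustered on family.
- **School, in both.** Enter it as a fixed factor, centred where the intercept is tested. Do not rely on a sandwich standard error over 4 schools: in simulations with a normal reference it rejected a true null 15% of the time under random loss and 26% under selective loss, against 5.5% and 6.7% with child-level standard errors.
- **Missing second readings.** State how children with only a baseline reading are handled.

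The cost is a few sentences in the SAP and a different cluster specification, with three degrees of freedom for school. No new data are needed. For BMI, precision matches a child-level analysis (SE 0.71 against 0.70 in run 2). The self-efficacy model may need extra programming where software uses one identifier for both the working correlation and the robust standard error.

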COVER PAGE

Study Title: Addressing Health Disparities in Childhood Obesity, One Summer at a Time

Clinical Trials Registration Number: NCT03595332

Date of document: April 15, 2018

Study Protocol

Background

Childhood obesity is one of the most urgent health challenges of our time. Obesity rates of Native American and Hispanic children are far higher than national averages, placing these children at high risk for early mortality, cardiovascular and metabolic conditions including diabetes, depression and overall poor quality of life.¹⁻³ By the 5th grade, approximately 50% of Hispanic and Native children are already overweight, and Native children have type 2 diabetes rates 9 times higher than non-Hispanic Whites.⁴ In our area, obesity rates are highly concentrated: most obese and overweight children are enrolled in 4 of the 10 elementary schools, which include primarily underserved Hispanic and Native American children.

Recent research has further demonstrated that the 'obesity gap' facing minority students is largely due to summer weight gain.⁵⁻⁹ Based on local data, it was confirmed that children in our school district were much more likely to worsen their weight-related health status during the summer than during the schoolyear. However, statewide, only 22% of children participate in summer activities, despite 65% of parents expressing interest.¹⁰ Finally, ages 7 to 11 have been found in national data to see a sharp increase in obesity rates.¹¹ Indeed, locally in 2015, approximately 20% of 7 year-olds are overweight or obese, but 35% of 11-year olds. Thus, we know which populations are at highest risk, at what developmental age changes occur most rapidly (ages 7-11) and that interventions are most needed in the summer, but that this need is not being met.

A modest amount of research has evaluated summer programming, but almost none among Native Americans/Hispanics. In the early 2000s, the CDC developed a 'Summer Scorecard' intervention,¹² a partnership with local businesses to provide children with a 'scorecard' of subsidized or free local activities. The VSS has not been tested among Hispanic and Native American children. Therefore, this study assessed the effectiveness of the VSS among children ages 5-13 in the 4 highest risk schools in the Flagstaff area. Outcomes included body composition (BMI) percentile score, reported physical activity and self-efficacy using survey instruments previously developed and tested by the CDC.

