Demographic variables. Child's age (in years), sex (male or female), ethnicity (American Indian/Alaskan Native, Hispanic, White, Black/African American, Native Hawaiian/Pacific Islander or Two or more), grade level and school membership were collected by the school district. Height and weight were collected at each school during the school day by a community outreach coordinator trained in research quality measurements, supported by the school nurse and volunteers. Children were asked to take shoes and jackets off and items out of their pockets. Height to the nearest quarter inch was measured twice with a Charder HM200P Portstad Portable Stadiometer. Weight was measured to the nearest 0.1 pounds with a Health O Meter 752KL Heavy Duty Remote Display Digital Scale. Children's first weight status was considered their baseline, with $\leq 5^{\text{th}}$ BMI percentile for their age and sex considered underweight, 5^{th} to 85^{th} percentile healthy weight, $\geq 85^{\text{th}}$ percentile overweight and $\geq 95^{\text{th}}$ percentile as having obesity

Behavioral constructs. Health behavior constructs (13 questions) aligned with Social Cognitive Theory were assessed. Key constructs include self-efficacy ("I think I can be physically active even if it is hot or cold outside."), social norms (example: "My friends think that doing physical activity is fun"), and access or barriers to participation in physical activity and summer programs ("There are lots of places near where I live where I can do physical activities").

Reported activity and sedentary behaviors. A total of 8 questions ask about participation in the VERB program, types of activity in the past 7 days and participation in other summer programs. The number of activities reported were counted and compared before and after the intervention.

Recruitment:

Children were recruited directly at each school by research staff in collaboration with school physical education or health and wellness instructors. Recruitment occurred by providing flyers and tables at school events and drop-off/pick up. Parents were provided with a consent form and children with an assent form explaining the risks and benefits. English and Spanish versions were available. Upon completion of both forms, participants were measured and surveyed (see measurements below).

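### The 10-week immediate-versus-delayed comparison omits baseline BMI percentile; if the response is one change score per child and assignment was random, adding it is a small, nearly free refinement

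*SAP*

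**What the plan says.** In the SAP's primary analysis, "we propose to test the difference in Body Mass Index (BMI) Percentile-scores for age and sex" between baseline and 10 weeks by a linear GEE, "adjusting for age (included as a covariate) and sex and ethnicity (included as factors"). The two groups are compared "by including a variable denoting immediate vs delayed group membership". No other analysis in the SAP names a group term, and none lists baseline BMI percentile as a covariate.

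The baseline value is available. Under Measures, the protocol says that children's "first weight status was considered their baseline", from measured height and weight. The SAP's second primary analysis already uses it: the highest-risk children are "defined as those participants with a baseline BMI Percentile score equal to or greater than the 85th percentile".

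Two things are not stated. The SAP does not say whether the data hold one change score per child or one row per visit. Its wording, and the fact that clustering is named for schools and families but not for visits within a child, fit a change score best. Neither document says how children came to be in the immediate or the delayed group.

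**The concern.** A change score removes most of a baseline difference between groups, but not all of it. Children who start high tend to fall and children who start low tend to rise, so change is negatively related to baseline. If one group starts higher by chance, part of that difference stays in the group coefficient. Baseline also explains some of the spread in change, and leaving it out gives up a little precision.

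This matters for one estimate only, but it is the estimate that separates the program from ordinary summer change. The size of the loss decides whether this is a defect or a refinement.

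**Working it through.** **Inputs.** From the protocol's sample size section: 80 children per arm analysed, two-sided alpha 0.05, a difference of 0.3 BMI units, and annual BMI change "with a standard deviation that varies across ethnic groups and years from 0.80" to 1.00. Assumed, because no document gives it: a cross-sectional BMI SD of 2 to 4 kg/m2, equal at both visits.

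**The plan's own figure first.** The protocol claims at least 80% power with "a sample size of 80 children per arm (a retention rate of 67"%). With SD 1.0, 0.3 / (1.0 × √(2/80)) = 1.897, which gives power of 47.5%. With SD 0.80 it is 66.0%. The stated power is not reproduced.

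**Correlation.** For equal variances, SD_change² = 2·SD²·(1 − ρ), so ρ = 1 − SD_change² / (2·SD²).

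**Gain from adding baseline.** The unadjusted change has variance 2·SD²·(1 − ρ). After adjustment for baseline it is SD²·(1 − ρ²). The ratio is (1 + ρ)/2.

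| SD of change | BMI SD | ρ | Variance ratio | CI width ratio | Power without baseline | Power with baseline |
|---|---|---|---|---|---|---|
| 1.0 | 2 | 0.875 | 0.9375 | 0.968 | 47.5% | 50.0% |
| 1.0 | 3 | 0.944 | 0.972 | 0.986 | 47.5% | 48.6% |
| 1.0 | 4 | 0.969 | 0.984 | 0.992 | 47.5% | 48.1% |
| 0.8 | 2 | 0.92 | 0.96 | 0.980 | 66.0% | 67.7% |
| 0.8 | 3 | 0.964 | 0.982 | 0.991 | 66.0% | 66.8% |
| 0.8 | 4 | 0.98 | 0.99 | 0.995 | 66.0% | 66.4% |

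**Percentile scale.** The test is on percentile, not BMI, so the check was repeated by simulation. Normal z-scores were shifted so that 20%, 35% or 50% of children lie at or above the 85th percentile (shares taken from the protocol's Background), with ρ of 0.875, 0.95 and 0.98. The variance fell by 1.1% to 7.2%. The slope of change on baseline was −0.022 to −0.144, so about 2% to 14% of a baseline imbalance stays in the unadjusted contrast.

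**What a chance imbalance leaves behind.** An imbalance of k standard errors shifts the unadjusted contrast by k·√((1 − ρ)/2) of its own standard error. For k = 1 that is 0.10 (ρ = 0.98) to 0.25 (ρ = 0.875). With a baseline SD of 23.3 to 28.7 percentile points, one standard error of imbalance is 23.3 × √(2/80) = 3.7 to 28.7 × √(2/80) = 4.5 points.

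**Type I error given the imbalance.** With that shift and conditional SD √((1 + ρ)/2), the unadjusted test rejects a true null 5.0% of the time at k = 1. At k = 2 it rejects 7.1%, 5.9% and 5.3% of the time for ρ of 0.875, 0.95 and 0.98. An imbalance of at least two standard errors arises in about 4.6% of random allocations.

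**Clustering.** With sibling pairs, an assumed family correlation of 0 to 0.5 and family-robust standard errors, the variance fell by 0.3% to 6.5%. Overall type I error under random assignment was 4.8% to 5.3% with or without baseline. That statement covers family-level clustering only. With 160 children in 4 schools, assigned by child, robust errors clustered on school, normal critical values and an assumed school correlation of 0 to 0.05, type I error was about 18% to 20% with or without baseline.

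**The case against.** The strongest case against is that nothing is broken. A change score already uses baseline, the planned test is legitimate under random assignment, and a confidence interval at most about 3% narrower would change no decision. That stands, and it is why this is only a suggestion.

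The benefit also depends on two unstated facts, the data layout and the allocation. That stands too. With repeated percentiles baseline is already part of the response. Without random assignment the adjusted and unadjusted contrasts can answer different questions. If whole schools were assigned, the figures above do not apply.

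The size rests on an assumed BMI SD and on annual change in BMI units, whereas the test concerns percentile over 10 weeks. Over the shorter interval the correlation may be higher and the gain smaller. The 6.25% end needs the smallest assumed BMI SD together with the largest SD of change. No figure includes age, sex or ethnicity, so none is for the exact planned model. These limits stand, and most of them make the gain smaller or less certain.

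The group test is also an addition to a primary null that concerns change in participants. That is so, but it remains the SAP's only comparison between groups.

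A reader might infer that omitting baseline makes the test biased or invalid. The documents do not support this: under random assignment the change-score contrast is unbiased overall. The high error rate with school-clustered errors is unrelated, because it is the same with the covariate. A reader might also infer a dropout bias from the 67% retention, but nothing in either document suggests that retention differs by group and baseline weight.

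**Conclusion.** The point holds as a minor refinement, confined to the 10-week immediate-versus-delayed comparison. Adding baseline BMI percentile cuts the variance by about 1% to 6% and removes the roughly 2% to 14% of a chance imbalance that subtraction leaves. This assumes one change score per child, random assignment by child or family, and ρ of 0.875 to 0.98.

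It does not extend to the second primary, 1-year or self-efficacy analyses, which test change against zero without a group term. Nor does it repair the power shortfall: with an SD of 1.0, power rises from 47.5% to at most 50.0%. If robust errors are clustered on about 4 schools with normal critical values, the level is well above 5% either way, which is a separate problem.

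**What to change.** If the response is one change score per child, add to the SAP's primary analysis: *For the immediate-versus-delayed comparison only, baseline BMI percentile (mean-centred) is included as a covariate; the same comparison without it is also reported.* State which of the two is the main estimate.

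Timing and allocation decide the label. The protocol already speaks in the past tense ("this study assessed the effectiveness of the VSS among children ages 5-13") and the SAP is dated July 2022, so data may have existed when the plan was written. If data had been examined when the change is made, or if assignment was not random, keep the planned comparison as main and label the adjusted one a sensitivity analysis.

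If the model instead uses repeated percentiles, do not add baseline; the comparison is then the group-by-time coefficient. Leave the tests of change against zero as written.

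The cost is one degree of freedom, one extra analysis and one or two sentences. No new data are needed.

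### The primary analyses test change from zero; the immediate-versus-delayed comparison has no deciding role in the first primary and is not stated in the second

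*SAP*

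**What the plan says.** **First primary (SAP, primary analysis paragraph).** The 10-week change in BMI percentile is tested against zero, adjusted for age, sex and ethnicity. The group comparison follows as an addition: "We will also test whether the immediate intervention group was significantly different from the delayed intervention group", by means of a group-membership variable. The paragraph closes with its only written null: "We will test the null hypothesis that participants in the intervention did not significantly change their BMI Percentile-score". It is not clear whether this refers to the immediate group or to both groups pooled.

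**Second primary (SAP, next paragraph).** Here "we will test whether the BMI Percentile from baseline to 10-weeks was significantly different from zero among the highest-risk children", defined by a baseline at or above the 85th percentile. The model is described in one sentence: "GEE models will be used restricting the sample to children with overweight at baseline". No group variable, between-group test or covariate list is given.

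**Secondary analyses (SAP).** The 1-year BMI percentile and 10-week self-efficacy analyses also test change from zero and state no group term.

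**Protocol.** Sample Size calculations states power "to detect intervention effects between arms from one time point to the next". Background gives the aim as assessing effectiveness, and reports that "children in our school district were much more likely to worsen their weight-related health status during the summer than during the schoolyear".

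**The concern.** The study asks whether the programme works, and its sample size rests on a comparison of arms. Zero change is not the value expected under an ineffective programme. Children's weight status may drift over a summer with or without a scorecard. Background points to worsening, though only relative to the school year and with no size on the percentile scale.

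The second primary has a further problem. Children are selected because their baseline is high, so their average tends to fall at the next measurement with no intervention at all. Upward drift and regression to the mean pull in opposite directions, and the net bias is unknown in size and in sign.

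In the second primary the test against zero is the only one stated, so an ineffective programme could appear beneficial, harmful or neutral. In the first primary the two planned tests can disagree, and the SAP has no rule for which one counts.

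**Working it through.** **1. The plan's own figure.** The protocol states at least 80% power between arms with 80 retained per arm (80/120 = 67%), d = 0.3, two-sided 0.05. The noncentrality is 0.3 × √(80/2) = 1.897, which gives 47% power from the noncentral t. The figure does not reproduce. That is a separate problem, but it confirms that the planned contrast was between arms.

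**2. First primary: can the two tests disagree?** Take 80 per arm, SD of change 1, two-sided 0.05.

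- *No programme effect, both groups shift by δ SD.* The test against zero rejects with probability Φ(δ√n − 1.96) + Φ(−δ√n − 1.96). For δ = 0.1 this is 14.6% at n = 80 (0.1 × √80 = 0.894) and 24.4% with both groups pooled, n = 160 (0.1 × √160 = 1.265). For δ = 0.2 it is 43.2% and 71.6%. In simulation the between-group test stays at about 5%.
- *Real difference, opposite shifts of −0.15 and +0.15 SD.* In simulation the pooled test against zero rejects about 5% and the between-group test about 47%.

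So either test can be significant without the other. The shifts are assumed; the documents give none for BMI percentile over 10 weeks.

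**3. Second primary: inputs.**

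- Retained children: 2 × 80 = 160 (protocol, Sample Size calculations).
- Share at or above the 85th percentile: 20%, 35% or 50%. Background says "locally in 2015, approximately 20% of 7 year-olds are overweight or obese, but 35% of 11-year olds" and "By the 5th grade, approximately 50% of Hispanic and Native children are already overweight". These are population shares for particular ages or ethnic groups, not for the enrolled sample. They give 0.20 × 160 = 32, 0.35 × 160 = 56 and 0.50 × 160 = 80 children.
- Assumed: normal BMI z-scores with SD 1; baseline to 10-week correlation r of 0.95, 0.98 or 0.99; upward drift of 0, 0.05 or 0.1 z; no programme effect.

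**4. Second primary: expected change.** For share p, the selected children lie on average φ(z₁₋ₚ)/p above the population mean: 1.400, 1.058 and 0.798 for 20%, 35% and 50%. The expected z change is drift − (1 − r) × that distance. At zero drift it runs from −0.05 × 1.400 = −0.070 to −0.01 × 0.798 = −0.008. A drift of 0.05 or 0.1 z can therefore cancel or reverse it.

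**5. Second primary: rejection rates.** 20,000 simulated trials per setting. Follow-up z = mean + r × (baseline − mean) + noise + drift; change in percentile points; two-sided 0.05 one-sample t-test. Entries are % significant decrease / % significant increase (nominal 2.5 / 2.5).

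| Share (n) | r | Drift 0 | Drift 0.05 z | Drift 0.1 z |
|---|---|---|---|---|
| 20% (32) | 0.95 | 41.3 / 0.0 | 14.7 / 0.2 | 3.2 / 2.0 |
| | 0.98 | 18.9 / 0.1 | 1.7 / 3.5 | 0.0 / 26.4 |
| | 0.99 | 11.3 / 0.3 | 0.1 / 15.4 | 0.0 / 74.1 |
| 35% (56) | 0.95 | 50.6 / 0.0 | 15.2 / 0.2 | 1.9 / 3.1 |
| | 0.98 | 23.2 / 0.1 | 1.0 / 5.5 | 0.0 / 46.8 |
| | 0.99 | 13.4 / 0.2 | 0.1 / 26.9 | 0.0 / 93.4 |
| 50% (80) | 0.95 | 50.4 / 0.0 | 11.6 / 0.4 | 0.9 / 5.9 |
| | 0.98 | 23.4 / 0.1 | 0.5 / 8.4 | 0.0 / 64.3 |
| | 0.99 | 13.5 / 0.3 | 0.0 / 38.2 | 0.0 / 98.4 |

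Mean change runs from −1.7 to −0.2 percentile points at zero drift, and from −0.3 to +0.9 at 0.1 z. In the same settings a between-group t-test rejects 4.5% to 5.2%, provided both groups share the drift.

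**6. Power if the group contrast decides.** For d = 0.3 and a two-sample t-test: 13%, 20%, 26% and 47% at 16, 28, 40 and 80 per arm. The first three are half of 32, 56 and 80.

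**The case against.** - **The group comparison is already in the first primary**, with a model term, the 0.05 level and confidence intervals. This stands. The gap there is only that no deciding test is named, and none of the second-primary simulation bears on it.
- **The second primary may be meant to reuse the first model.** Its paragraph also omits age, sex and ethnicity, which every other analysis lists, so this is plausible. But the text does not say so, and the only test it states is against zero.
- **The protocol also allows for time contrasts.** Its worked effect is described as holding between groups or time points, and Measures has activity counts compared before and after. True, but this does not make zero the no-effect value, and the power statement itself refers to arms.
- **The magnitudes are assumed.** Drift, correlation, normality and subset size are not trial data, and the tests are unclustered and unadjusted t-tests, not the planned GEE. This stands: the figures show that the stated test can mislead, not by how much it does here.
- **The delayed group may not be a concurrent untreated control.** The documents do not settle this, so the remedy has to be conditional.
- **Power is low for the group contrast.** True, but low power does not turn a before-after test into evidence of effectiveness.

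**Conclusion.** The concern holds and needs to be fixed before any effectiveness conclusion is drawn. Confidence is medium, because the role of the delayed group is not documented. It weighs most on the second primary, where an uncontrolled test in children selected for high values is the only one stated. Under the assumptions above, an ineffective programme gives a false decrease in 11% to 51% of trials at zero drift, and a false increase in 2% to 98% at an upward drift of 0.1 z. The direction of error depends on a drift that the documents do not give. In the first primary the defect is narrower: two planned tests that can disagree, with no rule for which decides. None of this depends on the protocol's power figure.

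**What to change.** 1. State how the groups were assigned, and whether the delayed group was untreated over the same baseline-to-10-week period.
2. If it was untreated, make the deciding null for both primaries no immediate-versus-delayed difference in 10-week change in BMI percentile. Test it with the group term on the change score, or the group-by-time term if repeated measures are modelled.
3. Add that term to the second primary and to the self-efficacy model, where the same test against zero is used. Report within-group change as descriptive.
4. If it was not untreated, and for any result without a concurrent untreated group (including 1 year unless shown otherwise), label the result an uncontrolled before-after change and draw no effectiveness conclusion from it.
5. The protocol is in the past tense and the SAP is dated July 14, 2022, so data may already have been seen. If so, date and disclose the change, and also report the test stated in that SAP.

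**Cost.** SAP wording and a statement of assignment and timing; no new data. If there was no concurrent untreated group, only the labelling applies. The price is power: about 47% in the first primary and 13% to 26% in the second for d = 0.3, before clustering and covariate adjustment. That d comes from raw BMI, not the percentile endpoint.
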